3.6.4 Procedures by Visit

3.6.4.1 Screening Visit (21 to 30 Days Prior to Baseline Visit)

The following procedures and assessments will be performed at the Screening Visit, which is to occur 21 to 30 days prior to initiation of Alphanate ITI treatment:

- Informed consent
- Entrance criteria (Section 3.2.1) to determine subject eligibility
- Medical history/demography
- Prior and concomitant medications

CONFIDENTIAL

- Vital signs (temperature, pulse rate, respiratory rate, systolic and diastolic blood pressure)
- Height and weight
- Physical examination, excluding genitourinary examination
- Blood and urine samples for clinical laboratory assessments at central laboratory
 - Hematology: Hemoglobin, hematocrit, platelets, red blood cell count including red blood cell morphology, white blood cell count with differential, absolute reticulocyte count
 - Virus safety retain samples
 - Clinical chemistry: sodium, potassium, creatinine, chloride, calcium, BUN, bicarbonate, albumin, lactate dehydrogenase (LDH), AST, ALT, alkaline phosphatase (ALP), glucose, total bilirubin, indirect bilirubin
 - FVIII inhibitor titer blood sample
 - Urinalysis: pH, protein, glucose, ketones, bilirubin, nitrites, urobilinogen, blood, leukocyte esterase (with microscopic examination of urine sediment if abnormal)

Subjects are permitted to be rescreened once. Subjects who fail to meet eligibility criteria upon rescreening are screen failures and will not be eligible to participate in the study.

3.6.4.2 Baseline Visit

The following procedures and assessments will be performed at the Baseline Visit:

- Entrance criteria (Section 3.2.1) to confirm subject eligibility (eg, Screening inhibitor titer is <10 BU)
- Update medical history
- Adverse events
- Prior and concomitant medications
- Vital signs (temperature, pulse rate, respiratory rate, systolic and diastolic blood pressure)
- Weight
- Physical examination, excluding genitourinary examination
- Blood and urine samples for clinical laboratory assessments at central laboratory
 - Hematology: hemoglobin, hematocrit, platelets, red blood cell count including red blood cell morphology, white blood cell count with differential, absolute reticulocyte count
 - Virus safety testing blood samples
 - If necessary, in order to minimize total blood volume drawn per day, virus safety samples may be drawn the day prior to the Baseline Visit instead of combining with other baseline blood draws on a single day. However, these samples *must* be obtained prior to first dose of Alphanate.
 - FVIII inhibitor titer blood sample
 - Genotyping sample: only for subjects with no documented FVIII genotyping results available in their medical charts

- The genotyping sample may be obtained at the next scheduled clinic visit, if needed.
- Urinalysis: pH, protein, glucose, ketones, bilirubin, nitrites, urobilinogen, blood, leukocyte esterase (with microscopic examination of urine sediment if abnormal)
- Train and document training of subject/caregiver on Alphanate storage requirements, preparation instructions, and self/caregiver-administration of Alphanate.
- Issue diary and train subject/caregiver on its use.
- Administer first Alphanate treatment based on subject's current weight measured in the study center.
- Dispense Alphanate IP sufficient until next scheduled visit.

3.6.4.3 Week 2, Week 4, Week 6, Week 8, and Subsequent Monthly Visits During ITI Treatment Phase

The following procedures and assessments will be performed at scheduled visits at Weeks 2, 4, 6, 8, and monthly thereafter during the ITI Treatment Phase:

- Adverse events
- Concomitant medications
- Vital signs (temperature, pulse rate, respiratory rate, systolic and diastolic blood pressure)
- Weight
- FVIII inhibitor titer blood sample (assayed by central laboratory)
- Virus safety retain samples (Week 8 and Month 15 only)
- Review subject diary, assess treatment compliance, and retrain subject or caregiver as needed.
- Dispense Alphanate IP sufficient until next scheduled visit.

3.6.4.4 Additional Assessments at Months 6, 12, 18, 24, and 30 During ITI Treatment Phase

In addition to the procedures and assessments to be performed during the scheduled semimonthly and monthly visits during the ITI Treatment Phase, the following procedures and assessments will be performed at Months 6, 12, 18, 24, and 30 during the ITI Treatment Phase:

- Physical examination, excluding genitourinary examination
- Blood and urine samples for clinical central laboratory assessments
 - Hematology: hemoglobin, hematocrit, platelets, red blood cell count including red blood cell morphology, white blood cell count with differential, absolute reticulocyte count
 - Virus safety retain samples (Months 6 and 30 only)

- Clinical chemistry: sodium, potassium, creatinine, chloride, calcium, BUN, bicarbonate, albumin, LDH, AST, ALT, ALP, glucose, total bilirubin, indirect bilirubin
- Urinalysis: pH, protein, glucose, ketones, bilirubin, nitrites, urobilinogen, blood, leukocyte esterase (with microscopic examination of urine sediment if abnormal)

3.6.4.5 Factor VIII:C Pharmacokinetic Assessment Visits

When the first inhibitor titer result has been received indicating the subject may have attained complete immune tolerance, a second confirmatory inhibitor measurement is to be performed within approximately 2 weeks after the last assessment; at this next visit, a sample is also collected for measuring FVIII:C in vivo recovery.

At FVIII:C in vivo recovery visit, the following assessments will be performed:

- Adverse events
- Concomitant medications
- Vital signs (temperature, pulse rate, respiratory rate, systolic and diastolic blood pressure)
- Weight
- Review subject diary, assess treatment compliance, and retrain subject or caregiver as needed.
- FVIII inhibitor titer blood sample (assayed by central laboratory)
- FVIII:C in vivo recovery blood samples (assayed by central laboratory) as detailed below:
 - Immediately prior to Alphanate infusion
 - Administer Alphanate 50 IU/kg.
 - 15 to 30 minutes after the completion of the Alphanate infusion

Upon confirmation that FVIII:C in vivo recovery is $\geq 66\%$ of the predicted normal value, an additional visit will be scheduled to occur within approximately the following 2 weeks to determine FVIII:C half-life (Section 3.6.2.4).

Prior to the FVIII:C half-life assessment visit:

• Call the subject/caregiver to schedule the pharmacokinetic assessment visit and instruct subject/caregiver to stop Alphanate treatments for 72 hours prior to the FVIII:C half-life assessment visit. Also remind the caregiver of the need for 2 additional visits to obtain the 24-hour and the 48-hour pharmacokinetic samples.

At the FVIII:C half-life visit, the following procedures and assessments will be performed:

- Adverse events
- Concomitant medications

- Vital signs (temperature, pulse rate, respiratory rate, systolic and diastolic blood pressure)
- Weight
- Review subject diary, assess treatment compliance, and retrain subject or caregiver as needed.
- FVIII inhibitor titer blood sample immediately before Alphanate infusion (assayed by central laboratory)
- FVIII:C in vivo recovery and half-life blood samples (assayed by central laboratory) as detailed below:
 - Immediately prior to Alphanate infusion
 - Administer Alphanate 50 IU/kg.
 - 15 to 30 minutes after the completion of Alphanate infusion
 - 1 hour after completion of Alphanate infusion
 - 3 hours after completion of Alphanate infusion
 - 6 hours after completion of Alphanate infusion
 - 12 hours (±2 hours) after completion of Alphanate infusion
 - 24 hours (±4 hours) after completion of Alphanate infusion
 - 48 hours (±4 hours) after completion of Alphanate infusion

Note: Two additional visits to the study center are required to collect the 24-hour sample and the 48-hour sample, and the subject is not to receive additional Alphanate until the 48-hour blood sample has been taken unless treatment is required for a bleeding event.

Subjects should receive their daily dose of Alphanate after all pharmacokinetic blood samples have been taken, and subjects will continue to receive their daily dose until it is determined that complete immune tolerance has been achieved.

Upon receipt of the result of the FVIII:C half-life assessment:

The results of FVIII inhibitor titer, FVIII:C in vivo recovery, and FVIII:C half-life will be provided to the investigator. If the subject's FVIII:C half-life is ≥ 6 hours (in conjunction with negative inhibitor titers and FVIII:C in vivo recovery $\geq 66\%$), the subject is considered a complete success and is to enter the Prophylactic Phase and begin dose tapering as described in Section 3.3.1. If the subject has not met the criteria for complete immune tolerance, the subject will continue ITI treatments up to 33 months until complete immune tolerance is achieved.

In addition, all subjects achieving partial immune tolerance at the completion of 33 months of ITI will have FVIII:C in vivo recovery and half-life assessments. These assessments can begin at the Month 33 Visit or begin at a separate visit scheduled within approximately 2 weeks of the scheduled Month 33 Visit (following a 72-hour FVIII treatment-free period).

3.6.4.6 Month 33 During ITI Treatment Phase

Subjects who are treatment failures at Month 33 should be scheduled for the Early Termination Visit (Section 3.6.4.8) instead of the Month 33 Visit.

```
CONFIDENTIAL
```

For subjects who have achieved partial immune tolerance, the subject will undergo FVIII:C pharmacokinetic assessments at the Month 33 Visit. Alternatively, the pharmacokinetic assessments can be scheduled to begin at a separate visit following the Month 33 Visit. If FVIII:C pharmacokinetic assessments are to begin at the Month 33 Visit, a telephone call is to be made by the study center staff 4 days prior to the visit to instruct the partial success subject/caregiver to stop Alphanate treatments for 72 hours prior to the visit.

The following procedures and assessments will be performed at Month 33 during the ITI Treatment Phase for subjects who have achieved partial immune tolerance:

- Adverse events
- Concomitant medications
- Vital signs (temperature, pulse rate, respiratory rate, systolic and diastolic blood pressure)
- Weight
- Physical examination, excluding genitourinary examination
- Blood and urine samples for clinical central laboratory assessments
 - Hematology: hemoglobin, hematocrit, platelets, red blood cell count including red blood cell morphology, white blood cell count with differential, absolute reticulocyte count
 - Virus safety retain samples
 - Clinical chemistry: sodium, potassium, creatinine, chloride, calcium, BUN, bicarbonate, albumin, LDH, AST, ALT, ALP, glucose, total bilirubin, indirect bilirubin
 - Urinalysis: pH, protein, glucose, ketones, bilirubin, nitrites, urobilinogen, blood, leukocyte esterase (with microscopic examination of urine sediment if abnormal)FVIII inhibitor titer blood sample (assayed by central laboratory)
- Review subject diary, assess treatment compliance, and retrain subject or caregiver as needed.
- Perform FVIII inhibitor titer assessment and begin FVIII:C pharmacokinetic assessments (Section 3.6.4.5) or schedule a separate visit for the FVIII:C pharmacokinetic assessments.
- Remind subject to not receive Alphanate until completion of the pharmacokinetic assessments at 24 hours and 48 hours after in-clinic Alphanate administration.

3.6.4.7 Prophylactic Phase Visits

All subjects who have confirmed complete tolerization and have had FVIII:C pharmacokinetic assessments at the completion of the ITI Treatment Phase will enter the 12-month Prophylactic Phase and continue in this phase through completion. Subjects who have confirmed partial tolerization at the completion of 33 months of ITI treatment and have had FVIII:C pharmacokinetic assessments at the completion of the ITI Treatment Phase will enter the Prophylactic Phase (that includes dose tapering) and continue in this phase through completion. If relapse during the Prophylactic Phase is suspected based on FVIII inhibitor titer or FVIII:C recovery results, confirmatory assessments of FVIII inhibitor titer and

CONFIDENTIAL

FVIII:C recovery must be performed (assayed by central laboratory) within approximately 2 weeks to confirm relapse (Section 3.6.2.4).

The following procedures and assessments will be performed as detailed below during the Prophylactic Phase:

MONTHS 1, 2, 4, 8, AND 10 VISITS DURING PROPHYLACTIC PHASE

- Adverse events
- Concomitant medications
- Vital signs (temperature, pulse rate, respiratory rate, systolic and diastolic blood pressure)
- Weight
- Review subject diary, assess treatment compliance, and retrain subject or caregiver as needed
- FVIII inhibitor titer blood sample (assayed by central laboratory)
- FVIII:C in vivo recovery blood samples (assayed by central laboratory) as detailed below:
 - Immediately prior to Alphanate infusion
 - Administer Alphanate 50 IU/kg.
 - 15 to 30 minutes after the completion of Alphanate infusion
- Instruct subject and caregiver on tapering the dose regimen (during the taper period only) (Section 3.3.1).
- Dispense Alphanate sufficient until the next scheduled visit.

MONTHS 3 AND 6 VISITS DURING PROPHYLACTIC PHASE

- Adverse events
- Concomitant medications
- Vital signs (temperature, pulse rate, respiratory rate, systolic and diastolic blood pressure)
- Weight
- Physical examination at Month 6 visit only, excluding genitourinary examination
- Review subject diary, assess treatment compliance, and retrain subject or caregiver as needed
- FVIII inhibitor titer prior to in-center Alphanate dosing (assayed by central laboratory)
- FVIII:C in vivo recovery blood samples (assayed by central laboratory) as detailed below:
 - Immediately prior to Alphanate infusion
 - Administer Alphanate 50 IU/kg.
 - 15 to 30 minutes after the completion of Alphanate infusion
- Blood and urine samples for clinical central laboratory assessments

- Hematology: hemoglobin, hematocrit, platelets, red blood cell count including red blood cell morphology, white blood cell count with differential, absolute reticulocyte count
- Clinical chemistry: sodium, potassium, creatinine, chloride, calcium, BUN, bicarbonate, albumin, LDH, AST, ALT, ALP, glucose, total bilirubin, indirect bilirubin
- Urinalysis: pH, protein, glucose, ketones, bilirubin, nitrites, urobilinogen, blood, leukocyte esterase (with microscopic examination of urine sediment if abnormal)
- Dispense Alphanate sufficient until next scheduled visit.

MONTH 12 VISIT DURING PROPHYLACTIC PHASE

For subjects who have maintained complete or partial immune tolerance, this visit will include the pharmacokinetic assessment of FVIII:C recovery and half-life (analyses performed at central laboratory) to confirm absence of relapse and to obtain final FVIII:C pharmacokinetic data. Therefore, all subjects must be instructed to not receive Alphanate for 72 hours prior to the visit.

- Adverse events
- Concomitant medications
- Vital signs (temperature, pulse rate, respiratory rate, systolic and diastolic blood pressure)
- Weight
- Physical examination, excluding genitourinary examination
- Review subject diary and assess compliance.
- Virus safety blood samples and retains
- Blood and urine samples for clinical central laboratory assessments
 - Hematology: hemoglobin, hematocrit, platelets, red blood cell count including red blood cell morphology, white blood cell count with differential, absolute reticulocyte count
 - Clinical chemistry: sodium, potassium, creatinine, chloride, calcium, BUN, bicarbonate, albumin, LDH, AST, ALT, ALP, glucose, total bilirubin, indirect bilirubin
 - Urinalysis: pH, protein, glucose, ketones, bilirubin, nitrites, urobilinogen, blood, leukocyte esterase (with microscopic examination of urine sediment if abnormal
- FVIII inhibitor titer blood sample immediately before Alphanate infusion (assayed by central laboratory)
- FVIII:C in vivo recovery and half-life blood samples (assayed by central laboratory) as detailed below:
 - Immediately prior to Alphanate infusion
 - Administer Alphanate 50 IU/kg
 - 15 to 30 minutes after the completion of Alphanate infusion
 - 1 hour after completion of Alphanate infusion

- 3 hours after completion of Alphanate infusion
- 6 hours after completion of Alphanate infusion
- 12 hours (±2 hours) after completion of Alphanate infusion
- 24 hours (±4 hours) after completion of Alphanate infusion
- 48 hours (±4 hours) after completion of Alphanate infusion

Note: Two additional visits to the study center are required to collect the 24-hour sample and the 48-hour sample, and the subject is not to receive additional Alphanate until the 48-hour blood sample has been taken unless treatment is required for a bleeding event.

• Collect unused Alphanate before sending subject home after in-clinic Alphanate dosing.

3.6.4.8 Early Termination Visit

The following assessments and procedures will be performed for subjects who are withdrawn from the study for treatment failure or subjects who discontinue the study prematurely for any reason:

- Adverse events
- Concomitant medications
- Vital signs
- Weight
- Physical examination, excluding genitourinary examination
- Blood and urine samples for clinical laboratory assessments to be sent to the central laboratory
 - Hematology: hemoglobin, hematocrit, platelets, red blood cell count including red blood cell morphology, white blood cell count with differential, absolute reticulocyte count
 - Clinical chemistry: sodium, potassium, creatinine, chloride, calcium, BUN, bicarbonate, albumin, LDH, AST, ALT, ALP, glucose, total bilirubin, indirect bilirubin
 - FVIII inhibitor titer
 - FVIII:C in vivo recovery (Note: If FVIII:C in vivo recovery is ≥66%, separate visits must be scheduled at which time the assessment of FVIII:C half-life will be performed.)
 - Virus safety retain samples
 - Urinalysis: pH, protein, glucose, ketones, bilirubin, nitrites, urobilinogen, blood, leukocyte esterase (with microscopic examination of urine sediment if abnormal)
- Collect unused Alphanate

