3.2.1.2 Exclusion Criteria

A subject meeting any of the following exclusion criteria is not eligible for participation in the study:

- 1. The subject has acquired FVIII deficiency.
- 2. The subject has previously received ITI treatment.
- 3. The subject has a recent (within 1 month) history of central line infection at the time of Screening.
- 4. The subject has a high risk of cardiovascular, cerebrovascular, or thromboembolic event as judged by the investigator.
- 5. The subject is currently undergoing treatment with immunosuppressive drugs (eg, systemic corticosteroids), azathioprine, cyclophosphamide, high dose immunoglobulin, interferon, or the use of a protein A column or plasmapheresis and is unwilling to discontinue these treatments starting at the screening visit.
- 6. The subject has a known infection with human immunodeficiency virus (HIV) or has clinical signs and symptoms consistent with current HIV infection.
- 7. The subject has a known previous infection with hepatitis B virus (HBV) or hepatitis C virus (HCV) or has clinical signs and symptoms consistent with current HBV or HCV infection.
- 8. The subject has significant proteinuria, has a history of acute renal failure or severe renal impairment (blood urea nitrogen [BUN] or creatinine >2 times the upper limit of normal), or is receiving dialysis at Screening.
- 9. The subject has a value of aspartate transaminase (AST) or alanine aminotransferase (ALT) >2 times the upper limit of normal at Screening.
- 10. The subject has clinical evidence of any significant acute or chronic disease that, in the opinion of the investigator, may interfere with successful completion of the trial or place the subject at undue medical risk.
- 11. The subject has a history of anaphylaxis or severe systemic reaction to any plasma-derived or other blood products.
- 12. The subject has participated in another clinical trial of an Investigational Product (IP) within 30 days prior to Screening—imaging studies without investigative treatments are permitted—or has received any investigational blood product within the previous 3 months.
- 13. In the opinion of the investigator, the subject or caregiver may have compliance problems with the protocol or the procedures of the protocol.

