3.6.2.4 Factor VIII:C Pharmacokinetics

Assessment of FVIII:C pharmacokinetics involves an assessment of in vivo recovery and a half-life assessment in order to confirm disappearance of the inhibitor. When the first inhibitor titer result has been received indicating the subject may have attained complete immune tolerance, a second confirmatory inhibitor measurement is to be performed within approximately 2 weeks after the last assessment; at this next visit, a sample will also be collected for measuring FVIII:C in vivo recovery. Upon confirmation of FVIII:C in vivo recovery $\geq 66\%$ of the predicted normal value, a FVIII:C half-life assessment visit is to be scheduled within the following 2 weeks to occur 72 hours after the last Alphanate dose.

All partial success subjects will also undergo an assessment of FVIII:C pharmacokinetics (assessments of FVIII:C in vivo recovery and a half-life) to begin within approximately 2 weeks of or at their scheduled Month 33 ITI Treatment Phase visit.

GENERAL PROCEDURES

Factor VIII:C in vivo recovery

Factor VIII activity in vivo recovery sampling may occur without a 72-hour FVIII treatmentfree period but \geq 24 hours after the last FVIII treatment. Sampling for in vivo recovery is performed immediately before in-center dosing with 50 IU/kg Alphanate and is followed by a sample collected 15 to 30 minutes after the Alphanate dosing.

The predicted normal value of FVIII:C in vivo recovery is 2 IU/dL per IU/kg dosed.

For subjects with negative inhibitor titer levels, if in vivo recovery is <66% of the predicted normal value, the subject will continue ITI treatment, and the site is to assess in vivo recovery monthly until recovery is $\ge 66\%$ of the predicted normal value.

For subjects with negative inhibitor titer levels, if FVIII in vivo recovery is $\geq 66\%$ of the predicted normal value, the site is to schedule the visit for FVIII:C half-life assessment to occur within approximately 2 weeks, with instructions to caregivers to adhere to a 72-hour FVIII treatment-free period immediately prior to the half-life assessment visit.

Factor VIII:C half-life assessments

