3.6.3 Description of Laboratory Tests and Procedures

Detailed descriptions of laboratory test procedures are located in the study Laboratory Manual. Table 3-1 provides a summary of the laboratory tests conducted for this study.

Test Panel	Description	Location
Hematology ^b	Hemoglobin, hematocrit, platelets, red blood cell count including red blood cell morphology, white blood cell count with differential, absolute reticulocyte count	Central
Clinical Chemistry ^b	Sodium, potassium, creatinine, chloride, calcium, BUN, bicarbonate, albumin, LDH, AST, ALT, ALP, glucose, total bilirubin, indirect bilirubin	Central
Factor VIII Genotype ^{a, b}	Identification of specific hemophilia A genetic mutation. Samples will be shipped to a central laboratory and analyses may occur at a specialty laboratory.	Central
Factor VIII Inhibitor ^b	Nijmegen modified Bethesda assay method for inhibitor assay.	Central
Factor VIII:C In Vivo Recovery ^b	Blood collection predose and at 15 to 30 minutes after administration of Alphanate 50 IU/kg.	Central
Factor VIII:C Half-life ^b	Following 72-hour FVIII treatment-free period. Blood collection predose and at 15 to 30 minutes and 1, 3, 6, 12 (\pm 2), 24 (\pm 4), and 48 (\pm 4) hours after administration of Alphanate 50 IU/kg.	Central
Viral Nucleic Amplification Technology ^b	Baseline: ^e HAV RNA, HBV DNA, HCV RNA, HIV-1 RNA, and B19V DNA testing Screening and Postbaseline: ^d Collection of retain samples for HAV RNA, HBV DNA, HCV RNA, HIV-1 RNA, and B19V DNA testing	Central
Viral Serology Testing ^b	Baseline: ^e Hepatitis A antibody differential (IgM/IgG), hepatitis B core antibody differential (IgM/IgG), hepatitis C antibody, HIV-1/-2 + Group O antibody, and B19V antibody differential (IgM/IgG) testing Screening and Postbaseline: ^d Collection of retain samples for hepatitis A antibody differential (IgM/IgG), hepatitis B core antibody differential (IgM/IgG), hepatitis C antibody, HIV-1/-2 + Group O antibody, and B19V antibody differential (IgM/IgG) testing	Central
Urinalysis	Microscopic evaluation is done only with cause. pH, protein, glucose, ketones, bilirubin, nitrites, urobilinogen, blood, leukocyte esterase (with microscopic examination of the urine if abnormal)	Central

Table 3-1 Name, Description, and Location of Laboratory Tests and Procedures

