10 APPENDICES

Appendix 1 Schedule of Procedures

	Screening			ITI Trea	atment Phase	•		Prop	ohylactic P	hase	
	Visit	Baseline Visit	Weeks 2, 4, 6, 8,	Months 6,	Pharmac Assessme		Month 33 After	Months			Early
Procedures/Assessments	Day –30 to –21 From ITI Start	Day of ITI Start	and Then Monthly After ITI Start	12, 18, 24, and 30 After ITI Start	FVIII:C in vivo Recovery Visit	FVIII:C Half-life Visit ^a	ITI Start Pharmacokinetic Visit ^a	1, 2, 4, 8, and 10	Months 3 and 6	Month 12	Withdrawal
Informed consent	Х										
Entrance criteria	Х	Х									
Medical history/demography	Х	Х									
Adverse events		Х	Х	Х	Х	Х	Х	Х	Х	Х	Х
Prior ^c /concomitant medications	Х	Х	Х	Х	Х	Х	Х	Х	Х	Х	Х
Vital signs	Х	Х	Х	Х	Х	Х	Х	Х	Х	Х	Х
Height	Х										
Weight	Х	Х	Х	Х	Х	Х	Х	Х	Х	Х	Х
Physical examination	Х	Х		Х			Х		X d	Х	X
Hematology	Х	Х		Х			Х		Х	Х	Х
Clinical chemistry	Х			Х			Х		Х	Х	X
FVIII genotype sample		X e									
FVIII inhibitor titer sample ^f	Х	Х	X ^g	Х	X	Х	Х	Х	Х	Х	X
Virus safety testing samples	X ^h	X ^{h,i}	X ^h	X ^h			X ^h			X ^h	X ^h
Urinalysis	Х	Х		Х			Х		Х	Х	X
Issue/review diary and retrain as needed ^j		Х	Х	Х	Х	х	Х	Х	Х	Х	
Administer Alphanate in the study center		Х			Х	Х	Х	Х	Х	Х	
FVIII:C in vivo recovery ^k					Х	Х	Х	X ¹	X ¹	Х	Х
FVIII:C half-life ^m						Х	Х			Х	X ⁿ
Collect unused Alphanate										X	X
Dispense Alphanate		Х	Х	Х			Х	X °	X °		

- ^a This visit will be scheduled within approximately 2 weeks following the confirmation of FVIII:C in vivo recovery ≥66% of the predicted normal value. A reminder telephone call is to be made by the study center staff 4 days prior to the half-life visit date. The staff are also to remind the caregiver regarding the 2 additional study center visits needed (ie, at 24 hours and 48 hours, respectively) in order to collect half-life samples.
- ^b Up to last 12 months of bleeding history will be captured.
- ^c Up to last 12 months of treatments for bleeding events will be captured.
- ^d Physical examination is only performed at Month 6 of the Prophylactic Phase.
- ^e For subjects who do not have a documented FVIII genotype, a blood sample should be obtained at the Baseline Visit, or later clinic visit (if blood volumes at the Baseline visit are restrictive), and sent to the central laboratory for genotyping analysis.
- ^f The scheduled inhibitor titer sample should occur ≥24 hours after the last Alphanate dosing or at the maximum possible interval from the last dose of Alphanate.

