- ^g To accurately capture the peak inhibitor titer on ITI treatment, additional unscheduled visits for inhibitor titer measurements may occur during the first 3 months of ITI treatment.
- ^h Samples for hepatitis A, hepatitis B, hepatitis C, HIV, and parvovirus B19 viral NAT and serology will be collected at Baseline, prior to Alphanate administration, and analyzed for information only. Virus safety retain samples will be collected at Screening, Week 8, Month 6, Month 15, Month 30, and Month 33 of the ITI Treatment Phase, as well as at the last visit of the Prophylactic Phase, or at the Early Termination Visit for virus testing in the event that a subject exhibits clinical signs and/or symptoms of viral infection; additional samples for viral NAT and serology testing may be collected *only* if there are clinical signs and symptoms of viral infection during the study. For subjects who achieve complete immune tolerance before Month 33, a viral retain sample will be collected at their last visit during the ITI Treatment Phase, before entering the Prophylactic Phase.
- ⁱ If necessary, in order to minimize total blood volume drawn per day, virus safety samples may be drawn the day prior to the Baseline Visit instead of combining with other baseline blood draws on a single day.
- ^j Issue and train subject/caregiver on diary and importance of ongoing collection of Alphanate drug administration (date/clock time of start and end of infusion, dose/volume, rate, and treatment interruption) or other items.
- ^k When the first inhibitor titer result has been received indicating the subject may have attained complete or partial immune tolerance, a second confirmatory inhibitor measurement is to be performed within approximately 2 weeks after the last assessment; at this next visit, a sample is also collected for measuring FVIII:C in vivo recovery. FVIII:C in vivo recovery is determined from blood samples collected before dosing and at 15 to 30 minutes after completion of dosing of 50 IU/kg Alphanate.
- ¹ FVIII:C in vivo recovery is determined by the central laboratory during the Prophylactic Phase for subjects who achieved complete immune tolerance. Suspected relapse must be confirmed by a complete pharmacokinetic assessment (FVIII:C in vivo recovery and half-life) at a separate scheduled visit within approximately 2 weeks.
- ^m FVIII:C half-life will be performed after a 72-hour FVIII treatment-free period at the following times during the study:

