 - During the ITI Treatment Phase within approximately 2 weeks after the second consecutive inhibitor titer of <0.6 BU is achieved and FVIII:C in vivo recovery is confirmed to be ≥66% of the predicted normal value
 - At the end of the ITI Treatment Phase in subjects who have achieved partial immune tolerance
 - At the completion of the Prophylactic Phase at the Month 12 visit

CONFIDENTIAL

Page 63 of 70

• At separately scheduled visits after the Early Termination Visit, but only for subjects who have a FVIII:C in vivo recovery ≥66% of the predicted normal value

FVIII:C half-life is determined from blood samples collected before dosing and at 15 to 30 minutes and 1, 3, 6, 12, 24 (\pm 4), and 48 (\pm 4) hours after completion of dosing of 50 IU/kg Alphanate.

For subjects with a negative inhibitor titer level and FVIII:C in vivo recovery $\geq 66\%$ but with FVIII:C half-life <6 hours, the half-life assessment should be repeated approximately every 12 weeks, at the investigator's discretion, until the half-life is ≥ 6 hours.

- ⁿ FVIII:C half-life is to be performed at separately scheduled visits after the Early Termination Visit, but only for subjects who have a FVIII:C in vivo recovery ≥66% of the predicted normal value.
- ^o For complete and partial success subjects, the ITI dose will be tapered down in a step-wise manner over an 8- to 12-week period to reach a final prophylactic dose of 50 IU/kg every other day or 3 times per week.

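### The Early Termination Visit requires a recovery test, and so a 50 IU/kg Alphanate infusion, after every early withdrawal, with no exemption where re-exposure is contraindicated

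*Combined protocol and SAP*

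**What the plan says.** The protocol's Section 3.6.4.8 states that its listed procedures will be done for subjects "withdrawn from the study for treatment failure or subjects who discontinue the study prematurely for any reason". FVIII:C in vivo recovery is in that list. The attached note concerns only what follows a recovery of 66% or more: "separate visits must be scheduled at which time the assessment of FVIII:C half-life will be performed".

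Three places define recovery by an infusion:

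- Section 3.6.2.4: "Sampling for in vivo recovery is performed immediately before in-center dosing with 50 IU/kg Alphanate", with a second sample 15 to 30 minutes later.
- Table 3-1 in Section 3.6.3: "Blood collection predose and at 15 to 30 minutes after administration of Alphanate 50 IU/kg".
- Appendix 1, footnote k, attached to the recovery row: samples before dosing and "at 15 to 30 minutes after completion of dosing of 50 IU/kg Alphanate".

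The Appendix 1 recovery row is marked under Early Withdrawal. Footnote n adds that "FVIII:C half-life is to be performed at separately scheduled visits after the Early Termination Visit", restricted to subjects who reach the 66% recovery threshold.

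At entry, exclusion criterion 11 in Section 3.2.1.2 reads: "The subject has a history of anaphylaxis or severe systemic reaction to any plasma-derived or other blood products".

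**The concern.** Followed as written, the exit visit gives Alphanate again to a child who left the study because of a reaction to Alphanate. The protocol foresees such an exit. Section 3.9 allows withdrawal when staying in would harm the subject, Section 3.5.2 makes discontinuation due to adverse events a safety endpoint, and Section 4.3.8 lists hypersensitivity (including anaphylaxis) and thromboembolic events as being of special interest. A history that bars exposure at entry has no counterpart rule at exit.

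What is at stake is the safety of a small number of children and the quality of the instruction to sites. The analysis gains little from the infusion: for a subject who has already stopped treatment, an exit recovery value matters to the primary endpoint only if it would complete the criteria for complete immune tolerance.

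**Working it through.** The point is textual, and the plan states no figure to reproduce. The steps are these.

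1. **Who is covered.** Section 3.6.4.8 covers every premature discontinuation, whatever the reason. A withdrawal for anaphylaxis is included.
2. **What is required.** Recovery is listed without condition, and the schedule row is marked under Early Withdrawal.
3. **Whether it can be done without a dose.** It cannot. Section 3.6.2.4, Table 3-1 and footnote k all define recovery by samples before and after 50 IU/kg.
4. **Whether a second dose follows.** Predicted recovery is 2 IU/dL per IU/kg, so 50 IU/kg predicts 2 × 50 = 100 IU/dL, and the threshold is 0.66 × 100 = 66 IU/dL. A subject at or above it goes on to half-life visits. Under Section 3.6.2.4 these need another 50 IU/kg after 72 hours without FVIII.
5. **Whether any condition concerns safety.** The only condition on exit pharmacokinetics is the 66% threshold for the half-life step (Section 3.6.4.8 and footnotes m and n). The protocol does write exceptions elsewhere: Section 3.6.2.4 forbids extra Alphanate during half-life sampling but excepts treatment of a bleed.
6. **Whether another section gives relief.** Sections 3.3.1, 3.6.4.5, 3.6.4.9, 3.8, 3.9 and 4.3.8 contain no waiver. Section 7.2 lets the investigator deviate to remove an immediate hazard without prior approval, with the deviation explained and submitted afterwards.

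**Size of the dose for other withdrawals.** Against the daily ITI dose, 50/100 = 50% or 50/200 = 25%. For a subject leaving as a treatment failure, for noncompliance or at the family's request, the infusion adds nothing unusual.

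**What an exemption could cost the primary endpoint.** With 25 treated subjects, one subject is 1/25 = 4 percentage points. Section 5.1.3.1 declares success if the Clopper-Pearson 95% lower bound exceeds 10%. That bound is the 0.025 quantile of Beta(x, 25 − x + 1):

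| Complete successes | Lower bound |
|---|---|
| 6 of 25 | 9.4% |
| 7 of 25 | 12.1% |

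One omitted exit assessment could change the conclusion only at 6 versus 7 successes. Even then, it could do so only for a subject who would otherwise have met all three criteria in Section 3.5.1.2.

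**The case against.** The strongest reply is that no competent investigator would give the infusion, and that the protocol already leaves room to refuse. Section 7.2 permits immediate action without approval, Section 3.9 rests withdrawal on the investigator's view of the subject's well-being, and Section 4.3.7 asks what was done with Alphanate after each adverse event. These passages do show discretion over dosing. None of them waives the exit test, so withholding it remains a deviation from a stated requirement. A foreseeable contraindication is better handled as planned conduct.

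Section 4.1 sends the reader to the Investigator's Brochure, which is not among these documents and may list contraindications. A reader might infer that sites have no instruction at all. The documents do not support that, and the point is confined to this protocol's visit rule.

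A reader might also infer that at least one such re-exposure is likely. Assuming 1% to 5% of subjects withdraw for a reaction, the chance of at least one case in 25 runs from 1 − 0.99^25 = 22% to 1 − 0.95^25 = 72%. Those rates have no anchor in the documents, and exclusion criterion 11 argues for low ones. The range reflects only the assumption, and it says nothing about whether an investigator would actually infuse.

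It might further be inferred that nothing would oblige a site to record why the test was omitted. That is not so. Section 3.3.2.5 requires reasons for giving less than the full dose to be entered in the eCRF, and Section 7.2 requires deviations to be documented.

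Finally, Section 3.6.4.8 has no dosing line, and the row "Administer Alphanate in the study center", as extracted, carries no mark under Early Withdrawal, although it is marked in the other 6 of the 7 recovery columns. This could be read as meaning that no infusion is intended. Since recovery is required there and cannot be measured without a dose, the gap is clerical and does not create an exemption.

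**Conclusion.** The concern holds as a minor safety point about a stated rule. The exit visit requires one infusion after any early withdrawal, and a second if recovery reaches 66%, with no exemption for a subject in whom re-exposure is judged unsafe. The entry criteria bar the same history, and the only relief is a deviation under Section 7.2.

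The hazard is narrow. Exclusion criteria 4 and 11 remove subjects known to be at high risk, and the frequency of on-study cases cannot be estimated from the documents. The conclusion rests on reading Section 3.6.4.8 literally together with the definition of recovery given elsewhere in the protocol. It makes no claim about the content of the Investigator's Brochure. Confidence is high that the exemption is absent. How often its absence would matter in practice is unknown.

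**What to change.** Add one sentence to Section 3.6.4.8, and mirror it in Appendix 1 footnote n and in the early-termination bullet of footnote m:

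*Exit in vivo recovery and half-life are not performed if, in the investigator's judgement, re-exposure to Alphanate is contraindicated (eg, after withdrawal for hypersensitivity/anaphylaxis or a thromboembolic event); the reason is recorded in the eCRF, and the exit inhibitor titer is still collected.*

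The examples guide judgement and are not automatic bars. The titer stays for everyone because it needs no infusion. The recording step extends the duties already in Sections 3.3.2.5 and 7.2.

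Optionally, as a clerical alignment, mark the in-center dosing row under Early Withdrawal, subject to the same exemption.

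The cost is amendment wording in one section and two footnotes, plus an eCRF entry for the reason. Exit pharmacokinetics will be missing for a few safety withdrawals. A subject withdrawn during the ITI Treatment Phase without earlier qualifying pharmacokinetics then counts as not a complete success under Section 3.5.1.2.
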